#### **8.1.3** Assessing Severity of Adverse Events

The National Cancer Institute (NCI) Common Terminology Criteria for Adverse Events (CTCAE Ver 4.03; http://evs.nci.nih.gov/ftp1/CTCAE/CTCAE 4.03 2010-06-14 QuickReference 8.5x11.pdf) is used to assign severity scales to AEs.

They are:

Grade 1 = Mild

Grade 2 = Moderate

Grade 3 = Severe

Grade 4 = Life Threatening

Grade 5 = Death

Elevated lactate levels are an anticipated pharmacodynamic effect of OXPHOS inhibitors. It is currently unknown if such effects may lead to biological consequences, such as lactic acidosis or

associated symptoms. Safety and tolerability of IACS-010759 is the primary objective of this phase 1 clinical trial. During this study, if elevated lactate levels are observed and subjects are hospitalized for observation of signs and symptoms (as described in Section 4.1.11), such hospitalization (or prolongation of hospitalization) for observation of signs and symptoms that would not otherwise require hospitalization will not be considered as a grade 3 toxicity when grading the severity of the adverse event if subjects remain asymptomatic and pH remains normal.

In addition, all AEs reported using the NCI CTCAE Ver 4.03 classification and graded as 4 or 5 are to be considered serious. The recommended Adverse Event Recording Guidelines are provided in Section 8.1.7.

The criteria for assessing severity are different than those used for seriousness.

#### 8.1.4 Assessing Relationship to Study Treatment

Items to be considered when assessing the relationship of an AE to the study treatment are:

- Temporal relationship of the onset of the event to the initiation of the study treatment
- The course of the event, considering especially the effect of discontinuation of study treatment or reintroduction of study treatment, as applicable
- Whether the event is known to be associated with the study treatment, or with other similar treatments
- The presence of risk factors in the study subject known to increase the occurrence of the event
- The presence of non-study treatment related factors which are known to be associated with the occurrence of the event

#### 8.1.5 Classification of Causality

**Causality** is a determination of whether there is a reasonable possibility that the drug may have caused or contributed to an adverse event. It includes assessing temporal relationships, dechallenge/rechallenge information, association (or lack of association) with underlying diseases, and the presence (or absence) of one or more likely causes.

The investigator must attempt to determine whether an adverse event is in some way related to the use of the study drug. This relationship should be described as follows:

**Unlikely:** The event is clearly due to causes distinct from the use of the study drug, such as a documented pre-existing condition, the effect of a concomitant medication, or a new condition that, based on the pathophysiology of the condition and the pharmacology of the study drug, is unlikely to be related to the use of the study drug.

**Possible:** The event follows a reasonable temporal sequence from administration of the study drug or the event follows a known response pattern to the study drug, *but* the event could have been produced by a concomitant medication or an intercurrent medical condition which, based on the pathophysiology of the condition and the pharmacology of the study drug, is unlikely to be related to the use of the study drug.

**Probable:** The event follows a reasonable temporal sequence from administration of the study drug and the event follows a known response pattern to the study drug and the event cannot be

reasonably explained by an intercurrent medical condition *or* the event cannot be the effect of a concomitant medication.

**Definite:** The event follows a reasonable temporal sequence from administration of the study drug, the event follows a known response pattern to the study drug, and based on the known pharmacology of the study drug, the event is clearly related to the effect of the study drug.

**Unknown:** Based on the evidence available, causality cannot be ascribed.

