### 4.3.2 Subject Evaluation & Statistics

The FAS will be used for evaluation of safety.

Adverse events will be coded using the MedDRA dictionary. Incidences of treatment-emergent adverse events (TEAE, those events that started after dosing or worsened in severity after dosing) will be presented overall and by maximum severity (according to CTCAE Ver 4.03) and relationship to study medication.

For each continuous laboratory parameter, results will be categorized as low, normal, or high based on the laboratory normal ranges. Frequencies and percentages will be presented by cohort for the shifts in these categories (i.e., low to normal, low to high, high to low, etc.) from baseline to each post-treatment assessment time point. Additionally, for each continuous hematology and chemistry parameter, descriptive statistics will be presented by cohort for the changes from baseline to each post-treatment assessment time point. Descriptive statistics will be presented by cohort for the changes in vital signs from baseline to each post-treatment assessment time point.

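### The causality scale in section 8.1.5 has no related category for a well-timed, unexplained toxicity without a known response pattern, so such an event could be left out of the DLT count

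*Combined protocol and SAP*

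**What the plan says.** Section 8.1.5 opens with a general test of reasonable possibility and then tells the investigator to describe the relationship with one of five categories:

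- **Unlikely** applies on this condition: "The event is clearly due to causes distinct from the use of the study drug". It thus needs a separate cause to be evident.
- **Possible** has two alternative ways in, namely "The event follows a reasonable temporal sequence from administration of the study drug or the event follows a known response pattern to the study drug", subject to the further condition that "the event could have been produced by a concomitant medication or an intercurrent medical condition".
- **Probable** needs reasonable timing "from administration of the study drug and the event follows a known response pattern to the study drug". Two exclusions follow, joined by *or*: an intercurrent condition does not reasonably explain the event, or "the event cannot be the effect of a concomitant medication".
- **Definite** needs reasonable timing, and "the event follows a known response pattern to the study drug, and based on the known pharmacology of the study drug", with no doubt left about the drug's role.
- **Unknown** is for this situation: "Based on the evidence available, causality cannot be ascribed".

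Three other provisions use the rating. Section 4.1.10 admits an event as a DLT only if it is rated Possible, Probable or Definite. Section 4.3.2 presents treatment-emergent events overall and also "by maximum severity (according to CTCAE Ver 4.03) and relationship to study medication". Section 8.1.7 asks for a written report within 24 hours for life-threatening or fatal events that are both unexpected and drug-related.

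**The concern.** A phase 1 trial of a new agent has to recognise toxicities that nobody has described before. For such an event, no earlier pattern exists and the informative facts are the timing and the absence of another cause. The scale gives those two facts no related category of their own. Probable and Definite both need a known pattern, and Possible needs a rival explanation. The ordering is therefore perverse: weaker evidence against the drug (a rival cause exists) earns a related label, and stronger evidence (no rival cause) earns none.

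At stake are the first-cycle DLT counts that drive the 3+3 rules in section 4.1.7 and the expansion boundary in Table 3 of section 4.1.8. The by-relationship tables and the 24-hour report are also affected. Under section 8.1.9 an event is unexpected if, among other things, it is not listed in the brochure. Unlisted events are the ones most likely to lack a known pattern.

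**Working it through.** **Step 1. Code the definitions.** Let T = reasonable timing, K = known response pattern, I = an intercurrent condition could explain the event, C = a concomitant medication could explain it, P = clear from known pharmacology.

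- Possible = (T or K) and (I or C)
- Probable = T and K and (not I *or* not C) as printed; T and K and (not I *and* not C) on a strict reading
- Definite = T and K and P
- Unlikely = clearly due to another cause

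**Step 2. Put cases in.**

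| Case | T | K | I | C | Possible | Probable | Definite | Unlikely |
|---|---|---|---|---|---|---|---|---|
| Novel, no other cause | 1 | 0 | 0 | 0 | no | no | no | no |
| Novel, co-medication could explain it | 1 | 0 | 0 | 1 | yes | no | no | no, unless clearly the cause |
| Known pattern, no other cause | 1 | 1 | 0 | 0 | no | yes | if P | no |
| Known pattern, illness could explain it | 1 | 1 | 1 | 0 | yes | yes as printed, no if strict | if P | no, unless clearly the cause |

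The first row meets no related category on either reading of Probable. The fourth row shows a smaller overlap: as printed, one event can meet both Possible and Probable.

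**Step 3. Look for a parse that escapes.** If the last *or* in Probable splits the whole sentence, Probable = (T and K and not I) or (not C), and the first row qualifies. The same parse makes every event not caused by a concomitant medication Probable, which cannot be intended.

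**Step 4. Follow the DLT count (sections 4.1.7 and 4.1.10).** Leaving out one event changes 1/3 to 0/3, so the next cohort may open without 3 more subjects. It changes 2/6 = 33% (MTD exceeded) to 1/6 = 17% (next cohort may start).

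**Step 5. Expansion phase (section 4.1.8).** The Table 3 boundary at the first look is 4 DLTs in 12. The stopping probability is P(X ≥ 4) with X ~ Binomial(12, p), and the average sample size is 12 × P + 18 × (1 − P). For p = 0.10, 0.15, 0.20, 0.25 and 0.30 this gives 0.0256, 0.0922, 0.2054, 0.3512 and 0.5075, with average sizes 17.8, 17.4, 16.8, 15.9 and 15.0. These are the Table 4 figures.

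Now suppose a share s of true DLTs is not counted, so the counted rate is p × (1 − s). The documents give no value for s; 25% and 50% are illustrative assumptions.

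| True rate | s = 0 | s = 25% | s = 50% |
|---|---|---|---|
| 0.20 | 0.205 | 0.092 | 0.026 |
| 0.30 | 0.507 | 0.276 | 0.092 |
| 0.40 | 0.775 | 0.507 | 0.205 |

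**The case against.** **Judgment language.** The opening of 8.1.5 includes dechallenge, rechallenge and the absence of likely causes. Section 8.1.4 lists five items to weigh, of which known association (with this or similar treatments) is only one. A sensible investigator could use these to rate the event as related, or could read known pattern broadly enough to include mechanism. This stands as practical mitigation. It works only by departing from or stretching the category definitions, none of which uses dechallenge or rechallenge.

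**Unknown is not a stated default.** The text never says that unexplained novel events go there, and the recording table in 8.1.7 has no row for Unknown. This also stands: the result is reached by elimination. It does not supply a related category.

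**Not every early toxicity lacks a pattern.** Raised lactate is an anticipated effect (8.1.3), and item 4 of section 4.1.11 declares its listed findings a DLT without repeating an attribution test. Peripheral neuropathy is already provided for by a baseline neurology examination and an exclusion criterion. The gap concerns events outside such provisions.

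**Frequency.** In relapsed AML an alternative cause can often be named, so the exact case may be uncommon.

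A reader might also infer that the scale removes new toxicities from view. The documents do not support that. All AEs are collected regardless of relationship (8.1.2), all SAEs are reported within 5 working days regardless of attribution (8.1.7), and TEAEs are also tabulated overall (4.3.2). The pause for subjects receiving less than 80% of planned dose has no relatedness filter (4.1.7), and the Safety Monitoring Committee may recommend changes at any time (4.1.14.1).

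A reader might further infer that the *or* in Probable turns illness-explained events into DLTs. It does not. An event clearly due to, say, sepsis fits Unlikely. Section 4.1.10 separately requires that a DLT be assessed as unrelated to intercurrent illness and concomitant medication. Possible and Probable also count alike for attribution, so no DLT count changes. For the same reason, a Possible label does not by itself make an event a DLT.

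**Conclusion.** The gap is real on the wording of 8.1.5. A well-timed novel event with no other cause fits no related category and, as written, cannot meet the attribution test in 4.1.10. It could therefore be missing from the 3+3 and Table 3 counts, from the related-event tables, and from the 24-hour report (leaving the 5-working-day SAE route if it is serious). It would still be recorded and seen by the Safety Monitoring Committee.

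The size is one event at a time: a single omission can decide a cohort of 3 to 6. The effect on the expansion boundary depends entirely on an unknown share of uncounted DLTs. At a true rate of 0.30, stopping at 12 subjects falls from 0.507 to 0.276 or 0.092 if that share is 25% or 50%. The conclusion assumes that investigators apply the definitions literally. The *or* in Probable is a secondary clarification affecting AE tables only.

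**What to change.** In section 8.1.5:

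1. Define Probable by reasonable timing and the exclusion of other causes, with a known response pattern as supportive evidence rather than a requirement. Keep the pattern requirement for Definite.
2. State that plausible timing with no alternative cause is at least Possible.
3. In the same edit, replace *or* with *and* between the two exclusions in Probable, so that both an intercurrent condition and a concomitant medication must be ruled out.

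With these changes the first row of the table in the working becomes Probable, and the fourth row no longer meets Probable. It would also help to state in 4.1.10 how an event rated Unknown is handled, and to align the 8.1.7 recording table with 8.1.5: the table has Unrelated and no Unknown, while 8.1.5 has the reverse.

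The cost is protocol wording and CRF completion guidance. The downside is that somewhat more events will be classed as related.

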### 8.1.6 Reporting Requirements

Reporting requirements will be as per institutional guidelines.

### Adverse events (AE) related to study conditions

The serious adverse event (SAE) reporting period will begin with the time of the first protocol-specific intervention (study drug administration) Regardless of severity or seriousness, new information regarding signs and symptoms that occurred prior to the first study medication dose on Day 1 should be recorded under the subject's Medical History.

AEs should be followed to resolution or stabilization, and reported as SAEs if they become serious. This also applies to subjects experiencing AEs that cause interruption or discontinuation of investigational product, or those experiencing AEs that are present at the end of their participation in the study. Such subjects should receive post-treatment follow-up as appropriate.

### 8.1.7 Serious Adverse Event Reporting (SAE)

An adverse event or suspected adverse reaction is considered "serious" if, in the view of either the investigator or the sponsor, it results in any of the following outcomes:

- Death
- A life-threatening adverse drug experience any adverse experience that places the subject, in the view of the initial reporter, at immediate risk of death from the adverse experience as it occurred. It does not include an adverse experience that, had it occurred in a more severe form, might have caused death.
- Subject hospitalization or prolongation of existing hospitalization
- A persistent or significant incapacity or substantial disruption of the ability to conduct normal life functions.
- A congenital anomaly/birth defect.

Important medical events that may not result in death, be life-threatening, or require hospitalization may be considered a serious adverse drug experience when, based upon appropriate medical judgment, they may jeopardize the subject or subject and may require medical or surgical intervention to prevent one of the outcomes listed in this definition. Examples of such medical events include allergic bronchospasm requiring intensive treatment in an emergency room or at home, blood dyscrasias or convulsions that do not result in subject hospitalization, or the development of drug dependency or drug abuse (21 CFR 312.32).

Important medical events as defined above, may also be considered serious adverse
events. Any important medical event can and should be reported as an SAE if deemed
appropriate by the Principal Investigator or the IND Sponsor, to the PROMETRIKA Safety
Manager.

- All events occurring during the conduct of a protocol and meeting the definition of a SAE must be reported to the IRB in accordance with the timeframes and procedures outlined in "The University of Texas M. D. Anderson Cancer Center Institutional Review Board Policy for Investigators on Reporting Unanticipated Adverse Events for Drugs and Devices". Unless stated otherwise in the protocol, all SAEs, expected or unexpected, must be reported to the PROMETRIKA Safety Manager, regardless of attribution (within 5 working days of knowledge of the event).
- All life-threatening or fatal events, that are unexpected, and related to the study drug, must have a written report submitted within 24 hours (next working day) of knowledge of the event to the PROMETRIKA Safety Project Manager.
- Unless otherwise noted, the entry of an AE that is designated as serious in the EDC system will automatically prompt an automated email alert for a newly entered case or for an existing case where a change in status of the AE fields has been made by the site. The email alert will be sent to relevant personnel involved with the SAE case management, including the PROMETRIKA Safety Manager. In the event that the site is unable to send the information through the EDC, the site will contact the Drug Safety Management department at PROMETRIKA by [contact]) or [contact]) and forward the SAE Form and other related documents to the PROMETRIKA Safety Manager. The site will be responsible for safety reporting to the MDACC IRB.
- Serious adverse events will be captured from the time of the first protocol-specific
  intervention (study drug administration), until 30 days after the last dose of drug, unless
  the participant withdraws consent. Serious adverse events must be followed until
  clinical recovery is complete and laboratory tests have returned to baseline, progression
  of the event has stabilized, or there has been acceptable resolution of the event.
- Additionally, all serious adverse events that occur after the 30 day time period that are related to the study treatment must be reported to the Sponsor and the PROMETRIKA Safety Manager. This may include the development of a secondary malignancy.

IACS2015-001: Protocol Amendment #11 (01-21-20)

### **Recommended Adverse Event Recording Guidelines**

	Recommend	ded Adverse	Event Record	ing Guideline	es
Attribution	Grade 1	Grade 2	Grade 3	Grade 4	Grade 5
, action					
Unrelated	Phase I	Phase I	Phase I Phase II	Phase I Phase II Phase III	Phase I Phase II Phase III
Unlikely	Phase I	Phase I	Phase I Phase II	Phase I Phase II Phase III	Phase I Phase II Phase III
Possible	Phase I Phase II	Phase I Phase II Phase III			
Probable	Phase I Phase II	Phase I Phase II Phase III			
Definitive	Phase I Phase II	Phase I Phase II Phase III			

#### 8.1.8 Reporting to FDA:

PROMETRIKA will submit **all** SAE reports to the IND Office via e-mail to [contact]. Serious adverse events will be submitted to FDA by the IND Sponsor (Safety Project Manager, IND Office) according to 21 CFR 312.32.

It is the responsibility of the PI and the research team to ensure serious adverse events are reported according to the Code of Federal Regulations, Good Clinical Practices, the protocol guidelines, the sponsor's guidelines, and Institutional Review Board policy.

### 8.1.9 Unexpected Adverse Event

An unexpected adverse event is one that is not listed in the current Clinical Investigator's Brochure (CIB) / Package Insert or that differs from the event mentioned in the CIB / Package Insert because of greater severity or specificity.

# 9 Appendices

# 9.1 Causes of elevated lactate

Shock	Pharmacological agents*
Distributive	Linezolid
Cardiogenic	Nucleoside reverse transcriptase inhibitors
Hypovolemic	Metformin
Obstructive	Epinephrine
Post-cardiac arrest	Propofol
Regional tissue ischemia	Acetaminophen
Mesenteric ischemia	Beta 2 agonists
Limb ischemia	Theophylline
Burns	
Trauma	Anaerobic muscle activity
Compartment syndrome	Seizures
Necrotizing soft tissue infections	Heavy exercise
Diabetic ketoacidosis	Excessive work of breathing
Drugs/toxins	Thiamine deficiency
Alcohols	Malignancy
Cocaine	Liver failure
Carbon monoxide	Mitochondrial disease
Cyanide	

Adapted from [23]

IACS2015-001: Protocol Amendment #11 (01-21-20) Page 55 of 59

### 9.2 List of abbreviations

AML Acute Myeloid Leukemia
ANC Absolute Neutrophil Count
CBC Complete Blood Chemistry

CR Complete Remission

CRi Complete Remission with Incomplete Hematological Recovery

CTCAE Common Terminology Criteria for Adverse Events

DDI Drug-drug interaction
DLT Dose-limiting Toxicity

eCRF Electronic Case Report Form

GCP Good Clinical Practice

HI Hematologic Improvement

IACS Institute for Applied Cancer Science

IB Investigator's Brochure
ICF Informed Consent Form

ICH International Conference on Harmonisation

IRB Institutional Review Board

LC-MS Liquid Chromatography—Mass Spectrometry

LSC Leukemic Stem Cells

MDACC MD Anderson Cancer Center MTD Maximum Tolerated Dose

MLFS Morphologic leukemia-free state
NOAEL No Observed Adverse Effect Level

ORR Overall Response Rate
OXPHOS Oxidative Phosphorylation

PD Pharmacodynamic PK Pharmacokinetic

pAMPK Adenosine Monophosphate Activated Protein Kinase

PI Principal Investigator
PR Partial Remission
RD Recurrence of Disease

RP2D Recommended Phase 2 Dose

QTcF Fridericia Correction Formula

SAE Serious Adverse Event
SCT Stem Cell Transplant
SD Standard Deviation
ULN Upper Limit of Normal

### 9.3 ECOG Performance Status\*

Grade	ECOG
0	Fully active, able to carry on all pre-disease performance without restriction
1	Restricted in physically strenuous activity but ambulatory and able to carry out work of a light or sedentary nature, e.g., light house work, office work
2	Ambulatory and capable of all selfcare but unable to carry out any work activities. Up and about more than 50% of waking hours
3	Capable of only limited selfcare, confined to bed or chair more than 50% of waking hours
4	Completely disabled. Cannot carry on any selfcare. Totally confined to bed or chair
5	Dead

\* As published in Am. J. Clin. Oncol.: Oken, M.M., Creech, R.H., Tormey, D.C., Horton, J., Davis, T.E., McFadden, E.T., Carbone, P.P.: Toxicity And Response Criteria Of The Eastern Cooperative Oncology Group. Am J Clin Oncol 5:649-655, 1982.

# 9.4 New York Heart Association (NYHA) Functional Classification

Class	Patient Symptoms
I	No limitation of physical activity. Ordinary physical activity does not cause undue fatigue, palpitation, dyspnea (shortness of breath).
II	Slight limitation of physical activity. Comfortable at rest. Ordinary physical activity results in fatigue, palpitation, dyspnea (shortness of breath).
III	Marked limitation of physical activity. Comfortable at rest. Less than ordinary activity causes fatigue, palpitation, or dyspnea.
IV	Unable to carry on any physical activity without discomfort. Symptoms of heart failure at rest. If any physical activity is undertaken, discomfort increases.

